Pediatric research in the management of nausea has been limited by the absence of a reliable method to quantify the intensity of this subjective symptom. In adults, the visual analog scale (VAS) is an accurate tool, but this has not been shown to be reliable in young children. By default the most common objective outcome measure used in pediatric studies has been the incidence and number of emetic episodes. This measure, however, correlates poorly with the somatic subjective symptom of nausea.

Apfel et al have shown that 30-40% of adult patients undergoing surgery have post discharge nausea and / or vomiting while 12% have vomiting. These data on nausea in adults were based on a visual analog scale for nausea. There are no data on the incidence of postoperative nausea in children since the severity of symptoms are difficult to measure as younger children are known to be unable to use the VAS reliably.

Recently a pictorial scale for measuring nausea, the Baxter Animated Retching Faces (BARF) scale, has been developed and shown to have construct, content and convergent validity as an instrument to measure nausea in children. The clinical usefulness of this scale in determining the incidence of postoperative and post-discharge nausea in children has yet to be determined including the lowest age where it can be used reliably, the score associated with a patient's perception of a need for treatment, the minimum change in the scores of clinical relevance and the test-retest reliability when nausea is rated as not having changed.

Section D: Purpose and Objectives

This study in the pediatric patient population is designed to determine: (1) The incidence of postoperative

nausea as compared to postoperative vomiting in the Post Anesthetic Care Unit (PACU) and on discharge (Post Discharge nausea and Vomiting). (2) The age related differences in the reliability and usefulness of the BARF and VAS scales for measuring nausea. (3) The minimal clinically relevant differences in nausea on the BARF and VAS scales. (4) The BARF and VAS scores associated with a patient's perception of the need for treatment. (5) The test - retest reliability of the VAS and BARF scores when nausea is rated as unchanged.

Section E: Protocol Risks/Subjects

E1. Risk Category

Category 1: Research not involving greater than minimum risk.

E2. Subjects

Gender:

Both

Age:

Adolescent (13-17 yrs), Child (3-12 yrs)

Ethnicity:

All Ethnicities

Primary Language:

English

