(1) Age > 3 years but below 18 years (2) Elective surgery (3) American Society of Anesthesiologists physical status 1-3 (Free from major concurrent disorders) (4) Free from nausea and / or vomiting in the previous 24 hours (5) Cognitive, visual, hearing and communicative ability to use the VAS as shown by the ability to complete a seriation task in which children pick the biggest of 6 cut out shapes, then the smallest, and the biggest remaining until no shapes remain (Beyer et al: J Pediatr Nurs 1992; 7: 335-46)

Exclusion Criteria:

(1) Developmental delay (2) Blindness (3) Impaired cognitive or communicative abilities including inability to rate the intensity of symptoms and failure to complete the seriation task (4) Surgical procedures which may result in diminished hearing or vision in the immediate postoperative period (5) Nausea and /or vomiting within 24 hours prior to the procedure (6) Inability to understand English, (7) Patient or parental refusal to participate (8) Pregnant females

F2. Procedure

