time points: (1) before induction of anesthesia, (2) when awake in the PACU, (3) just before, and (4) 30-60 mins after receiving analgesic or antiemetic therapy and (5) just before discharge home. The order of presentation of scales will be randomized but the same for all time points for an individual subject. After the first set of assessments are done in the PACU, patients will also be asked to rate their nausea on a 5 point Likert scale as : (1) Much worse than before, (2) A little worse than before, (3) The same as before (4) A little better than before and (5) Much better than before. They will also be asked if they want any treatment of their nausea. Another set of assessments will be just prior to discharge. All other aspects of patient management will be the standard care given to such children at the Texas Children's Hospital. Patients will be discharged from the PACU when they have achieved the standard criteria set for discharge at the TCH. At the time of discharge we will give the parents a diary to record the the MAXIMUM nausea on the VAS and BARF scales and mail it back in a stamped envelope. We will phone them about 24 hours after surgery and ask if the child had any nausea, vomiting and what medications were used after going home. We will ask the parent to rate their satisfaction with the control of nausea and with the entire perioperative experience on a 0-10 scale. We will remind them to mail the nausea assessments back and to state which face represented the maximum nausea after discharge.

Section G: Sample Size/Data Analysis

G1. Sample Size

How many subjects (or specimens, or charts) will be used in this study?

Local: 387 Worldwide: 387

Please indicate why you chose the sample size proposed:

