The study has a number of aims and the power analysis is provided separately for each aim: (1) In order to examine the age related ability to use the BARF scale we will recruit 28 subjects each in the ages of 3, 4, 5, 6, 7, 8, 9, 10, 11, 12 and >12 years years (28 X 11 = 308). Power analysis was based on an alpha of 0.05, power of 80% and a large effect size (Cohen's d = 0.80) as it was assumed a large difference would be needed for the results to have clinical utility (Pain 2011; 152: 1327-33). This suggested a group size of 24 would be needed. Allowing for a drop out rate of 20% we plan to recruit 28 in each of the 11 groups. (2) Power analysis for minimum clinically relevant difference in BARF scores: A one face difference in the BARF scale is the minimum difference that can be detected. A previous study showed that the mean BARF scores in the postoperative period in children was 1.6 +/- 2.4 (Pediatrics. 2011 Jun;127(6):e1542-9) . In order to detect a 1 face difference with 80% power at the 0.05 level of significance we will need 93 subjects who had a change in their nausea scores. Assuming an incidence of postoperative nausea and vomiting (PONV) of 33% (which is similar to previous data in children), a group size of 93 X3= 279 will be required to obtain 93 subjects with a change in nausea scores. We plan to recruit 387 subjects to allow for a 35% dropout rate.

This sample size will have a >80% power for the other aims of the study (The BARF and VAS scores associated with a patient's perception of the need for treatment and the test - retest reliability of the VAS and BARF scores when nausea is rated as unchanged.)

G2. Data Analysis

Provide a description of your plan for data analysis. State the types of comparisons you plan (e.g. comparison of means, comparison of proportions, regressions, analysis of variance). Which is the PRIMARY comparison/analysis? How will the analyses proposed relate to the primary purposes of your study?

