Statistical Analysis: (1) The mean and SD of all scores will be calculated along with their distribution. The incidence of postoperative nausea and postoperative vomiting in the PACU and after discharge (post-discharge nausea) will be calculated. The incidence of severe nausea (score>6 on the BARF scale) and severe vomiting (3 or more episodes over 24 hours) will also be determined. (2) We will record the age of a child and their ability to rate their nausea on the BARF and VAS scales to determine the minimum age where a patient can reliably use the scale. (3) Changes in BARF and VAS nausea scores will be calculated for subjects who report their nausea as a little worse than before or a little better than before, to determine the minimum change in scores of clinical relevance. (4) The BARF score and its relationship to the request for rescue antiemetics will be examined by a Spearman's rank correlation. (5) The relationship between the first and subsequent BARF and VAS nausea scores in patients who state their nausea is 'the same as before?' will be examined by a Spearman's rank correlation and a Cronbach's alpha calculation. This will provide the test ? retest reliability.

Section H: Potential Risks/Discomforts

Describe and assess any potential risks/discomforts; (physical, psychological, social, legal, or other) and assess the likelihood and seriousness of such risks:

The risks are limited to possible loss of confidentiality as there are no changes in surgical or anesthetic management of the child other than obtaining data on estimating the degree of nausea. Loss of confidentiality is unlikely in view of standard steps taken to avoid this.

Section I: Potential Benefits

Describe potential benefit(s) to be gained by the individual subject as a result of participating in the planned work.

Subjects will not have any direct immediate benefits from participating in these studies.

Describe potential benefit(s) to society of the planned work.

Determining the clinical utility of a faces pain scale will facilitate treatment and research into this clinically important realm of suffering for children of all ages. Future patients may benefit from having such a tool as it will permit clinicians to measure the symptom severity and then treat such patients

Do anticipated benefits outweigh potential risks? Discuss the risk-to-benefit ratio.

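### Test-retest reliability (G2, item 5) is planned without any agreement statistic, and Cronbach's alpha from two ratings overstates the reliability of a single rating

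*Combined protocol and SAP*

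**What the plan says.** Section D lists as its fifth objective "The test - retest reliability of the VAS and BARF scores when nausea is rated as unchanged". G2 item (5) takes the children who report no change and says that the relation between their first and later scores on each scale "will be examined by a Spearman's rank correlation and a Cronbach's alpha calculation". It adds that this supplies the test-retest reliability. No ICC, kappa, paired difference, limits of agreement or within-child SD is named anywhere.

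Two other items in G2 come close but do not fill the gap:
- Item (1): "The mean and SD of all scores will be calculated along with their distribution". This is neither paired nor restricted to the unchanged children.
- Item (3) calculates change scores, but only for children who report being a little worse or a little better.

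On timing, F2 says: "After the first set of assessments are done in the PACU, patients will also be asked to rate their nausea". It does not say what the comparison point is. G1 states: "A one face difference in the BARF scale is the minimum difference that can be detected".

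**The concern.** Test-retest reliability asks whether a child whose nausea has not changed gives the same score twice. Spearman's correlation compares rank order, and alpha is built from variances and covariances. Both can be high when the scores themselves differ.

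Alpha has a second problem. From two ratings it describes the reliability of their sum, whereas in F2 and in clinical use the scale is read one rating at a time. The two planned statistics can therefore give quite different figures on the same data, and the plan does not say which is the result.

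The scatter of unchanged children, in scale points, is what a reader needs beside the one-face difference in G1 and the minimum relevant change sought in item (3). The plan does not report it directly.

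**Working it through.** **The plan's own figure.** The only figure attached to this aim is G1's claim of more than 80% power for the remaining aims. It cannot be reproduced: no target coefficient, null value or number of unchanged children is given.

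**Inputs.**
- From G1: "the mean BARF scores in the postoperative period in children was 1.6 +/- 2.4".
- Assumed, because the documents do not give them: six faces scored 0, 2, 4, 6, 8, 10, with probabilities 0.586, 0.200, 0.108, 0.058, 0.031, 0.017. These were chosen to reproduce that mean and SD with a declining shape.
- The documents give no shift size, direction or error rate, so the scenarios below are illustrations.

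**Step 1: alpha from two ratings.** With variances s1² and s2² and covariance c, alpha = 4c/(s1² + s2² + 2c). With equal variances and correlation r this becomes alpha = 2r/(1 + r), so r = alpha/(2 − alpha).
- Alpha 0.70: 0.70/1.30 = 0.54
- Alpha 0.80: 0.80/1.20 = 0.67
- Alpha 0.90: 0.90/1.10 = 0.82

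This is algebra and needs no assumption about the trial's data beyond equal variances.

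**Step 2: a uniform shift.** Adding a constant d to every second rating changes neither ranks nor covariances. If the ratings otherwise agree perfectly, the single-rating absolute-agreement ICC is s²/(s² + d²/2). With s = 2.4 and d = 2 (one face on the assumed scoring): 5.76/(5.76 + 2) = 0.74. Capping at 10 brings this to 0.73.

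**Step 3: simulation on the assumed six-face scale** (300,000 pairs per scenario, scores kept within 0 to 10).

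| Scenario | Spearman | Alpha | ICC | Same face twice |
|---|---|---|---|---|
| Every child one face higher | 1.00 | 1.00 | 0.73 | – |
| Half the children one face higher | 0.84 | 0.96 | 0.85 | 51% |
| Every child one face lower, floored at 0 | 0.81 | 0.94 | 0.82 | 59% |
| No shift; each rating off by one face, 20% each way | 0.69 | 0.91 | 0.83 | 59% |

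In the first row neither planned statistic registers the shift. In the other three, alpha is 0.91 or more although only 51% to 59% of children choose the same face twice. Spearman in those rows is slightly or clearly below the ICC.

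**Step 4: scatter in points.** With no shift, within-child SD = s√(1 − r). At alpha 0.80 and s = 2.4 this is 2.4 × √(1 − 0.667) = 1.4 points. It is 0.87 if s is 1.5 and 1.85 if s is 3.2. The SD among unchanged children is not in the documents, so a reported alpha alone does not yield this figure.

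**Step 5: which pair.** Inclusion criterion (4) in F1 requires children to be "Free from nausea and / or vomiting in the previous 24 hours". If the comparison point is the preoperative baseline, an unchanged child is mostly one who still has no nausea, and any coefficient would say little. If it is an earlier PACU rating, F2 needs to say that the change question is asked at the later one.

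**The case against.** **The plan does not rely on alpha alone.** Spearman is reported beside it, is not stepped up, and in three of the four scenarios is lower than the ICC. This stands. A reader might infer that both planned statistics flatter the scale; the figures do not support that, and the overstatement concerns alpha only. A lower Spearman still does not show whether the cause is a shift, random error or tied scores.

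**A shift need not be invisible.** On scores with 59% zeros, a downward shift is clipped at the floor and Spearman falls about as far as the ICC (0.81 against 0.82). This also stands. A reader might infer that any systematic shift goes undetected, or that one is expected here. The first is true only of a shift not clipped at the scale ends, and the documents give no reason to expect the second.

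**The information is partly recoverable.** Single-rating consistency follows from alpha by the formula in Step 1, and the raw scores would allow an ICC later. True, but the back-calculation assumes equal variances and says nothing about a shift, and item (1) does not promise the unchanged children's paired scores.

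**Precision.** From "a group size of 93 X3= 279 will be required to obtain 93 subjects with a change in nausea scores" one might infer that the remaining 279 − 93 = 186 children assure a precise ICC. The documents do not support this. By G1's reasoning these are mainly children without postoperative nausea or vomiting, so many pairs may be zero at both ratings. The usual normal-theory interval also under-covers on such scores: about 88% for a nominal 95% at n = 186 in the 20% error scenario.

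**The undefined pair is a separate gap.** It would remain under any coefficient, so it is secondary here and belongs with the fix.

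**Conclusion.** The point holds in this form: the plan makes two statistics the whole test-retest result, neither measures agreement, and alpha from two ratings overstates single-rating reliability (0.80 means 0.67). The step-up rests only on equal variances. The size of the shift effect (ICC 0.73 with both planned statistics at 1.00) rests on an assumed one-face upward shift, assumed face spacing and an assumed score distribution matched to G1. Severity is minor to moderate: this is one of five aims, no decision rule depends on it, and the collected scores would support a better analysis if the change question accompanies the second rating of the pair.

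**What to change.** In G2 item (5), for BARF and VAS separately:
- Replace alpha with the single-rating absolute-agreement ICC (two-way model), or weighted kappa for BARF, as the named main statistic, with a bootstrap 95% confidence interval.
- In the children reporting no change, add the paired mean difference and within-child SD and, for BARF, the percentages choosing exactly the same face and within one face.
- Keep Spearman as descriptive.
- State which two ratings form the pair, and make F2's timing of the change question consistent with it.
- Report the percentage of pairs that are zero at both ratings, since this affects any coefficient, the ICC included.

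The cost is a few lines of text, a little more analysis and, depending on the pair chosen, asking the change question once more. The reported figure will probably look less flattering than alpha. Clinical management is not affected.
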